6.3.1.2 Urinalysis

Analysis Set: Safety Analysis Set Analysis Variable(s) : pH

	-	
	Specific Gravity	
	Protein	[-, +-, 1+, 2+, 3+, 4+, 5+]
	Glucose	[-, +-, 1+, 2+, 3+, 4+, 5+]
	Occult blood	[-, +-, 1+, 2+, 3+, 4+, 5+]
	Ketones	[-, +-, 1+, 2+, 3+, 4+, 5+]
	Urobilinogen	[-, +-, 1+, 2+, 3+, 4+, 5+]
	Bilirubin	[-, +-, 1+, 2+, 3+, 4+, 5+]
Categories:	Intensity	[Grade 0, Grade 1, Grade 2, Grade 3, Grade 4]

Visit:	(1), (2), and (3):
	Baseline, WK5D1, WK9D1, WK13D1, WK25D1, WK49D1, WK61D1,
	WK73D1, WK85D1, WK97D1, SFU

Analytical

Anarytical			
Method(s) :	For pH and specific gravity, summaries (1) and (2) will be provided by		
	treatment group.		
	For each variable other than pH and specific gravity, summary (3) will be		
	provided by treatment group.		
	For protein, summaries (4) and (5) will also be provided by treatment group.		
	(1) Summary of Urine Laboratory Test Results and Change from Baseline		
	by Visit		
	Descriptive statistics for observed values and changes from baseline		
	will be provided for each visit.		
	(2) Case Plots		
	Plots over time for each subject will be presented.		
	(3) Number of Subjects in Categories of Urine Laboratory Test Results		
	Shift tables showing the number of subjects in each category at baseline		
	and each post-baseline visit will be provided.		
	(4) Number and Percentage of Subjects with Urine Laboratory Test		
	Abnormalities by Grade		
	Frequency distributions for each urine laboratory test abnormality will		
	be provided by grade. Evaluable data (i.e., non-missing and acceptable		
	according to the Handling Rules for Analysis Data) obtained after		
	baseline will be used. A subject with multiple occurrences of laboratory		
	test abnormality will be counted once for the abnormality with the		
	maximum intensity.		
	(5) Maximum Grade Shift From Baseline of Urine Laboratory Parameters		
	The maximum post-baseline grade will be determined for each subject.		
	Shift tables showing the number of subjects in each grade category at		
	baseline and post-baseline visit will be provided using evaluable data		
	(i.e., non-missing and acceptable according to the Handling Rules for		
	Analysis Data).		

6.3.2 Vital Signs, Physical Findings, and Other Observations Related to Safety

6.3.2.1 Vital Signs and Weight

8	8
Analysis Set:	Safety Analysis Set
Analysis	
Variable(s) :	Body Temperature (C)
	Systolic Blood Pressure (mmHg)
	Diastolic Blood Pressure (mmHg)
	Pulse (bpm)
	Weight (kg)
Visit:	(1) and (2):
	Baseline, WK2D1, WK3D1, WK5D1, WK9D1, WK13D1, WK25D1,
	WK49D1, WK61D1, WK73D1, WK85D1, WK97D1, SFU
Analytical	
Method(s) ·	For each variable summaries (1) and (2) will be provided by treatment

Method(s): For each variable, summaries (1) and (2) will be provided by treatment group. For applicable variables, summary (3) will be provided by treatment group.

- Summary of Vital Signs and Weight Parameters and Change from Baseline by Visit Descriptive statistics for observed values and changes from baseline will be provided for each visit.
- (2) Case PlotsPlots over time for each subject will be presented.
- (3) Number and Percentage of Subjects with Markedly Abnormal Values of Vital Signs Parameters Overall frequency distributions of MAV will be provided. If a vital sign

parameter has both lower and upper MAV criteria, analysis will be performed for each. Further details are given in Appendix.

6.3.2.2 12-lead ECG

Analysis Set:	Safety Analysis Set	
Analysis		
Variable(s) :	Heart Rate (bpm)	
	RR Interval (msec)	
	PR Interval (msec)	
	QRS Interval (msec)	
	QT Interval (msec)	
	QTcF Interval (msec)	observed value: [Min<= - <=449, 450<= - <=479,
		480<= - <=499, 500<= - <=Max]

		change from baseline :
		[Min<= - <=29, 30<= - <=59, 60<= - <=Max]
	QTcB Interval (msec)) observed value: [Min<= - <=449, 450<= - <=479,
		480<= - <=499, 500<= - <=Max]
		change from baseline :
		[Min<= - <=29, 30<= - <=59, 60<= - <=Max]
	12-Lead ECG	
	Interpretation	[Within Normal Limits, Abnormal but not Clinically
		Significant, Abnormal and Clinically Significant]
Visit:	(1), (2), and (4):	
	Baseline, WK3D1, W	/K5D1, WK25D1, WK49D1, WK73D1, WK97D1, SFU
Analytical		
Method(s) :	For each variable oth	er than 12-lead ECG interpretations, summaries (1) and
	(2) will be provided b	by treatment group.
	For applicable variab	les, summary (3) will be provided by treatment group.
	For 12-lead ECG inte	erpretation, summary (4) will be provided by treatment
	group.	
	(1) Summary of EC	CG Parameters and Change from Baseline by Visit
	Descriptive stat	istics for observed values and changes from baseline
	will be provided	d for each visit. Frequency distributions for the
	categorical vari	ables will be provided for each visit.
	(2) Case Plots	
	Plots over time	for each subject will be presented.
	(3) Number and Pe	rcentage of Subjects with Markedly Abnormal Values of
	ECG Parameter	'S
	Overall frequen	cy distributions of MAV will be provided. If an ECG
	parameter has b	both lower and upper MAV criteria, analysis will be
	performed for e	each. Further details are given in Appendix.
	(4) Summary of Sh	ifts of ECG Parameters
		wing the number of subjects in each category at baseline
	and each post-b	aseline visit will be provided.

6.3.2.3 Bone Mineral Density

Analysis Set: Analysis	Safety Analysis Set
Variable(s) :	(1) Bone Mineral Density (L ₂₋₄)
	(2) Bone Mineral Density (Femoral Neck)
	(3) Bone Mineral Density (Total Hip)
Visit:	Baseline, WK25D1, WK49D1, WK73D1, WK97D1
Analytical	
Method(s):	The following analysis will be performed using the safety analysis set.
	For (1) to (3), the descriptive statistics of the observed values and the
	two-sided 95% confidence intervals of the mean will be provided for each
	visit by treatment group. The same analysis will be performed for the percent
	change from baseline.

6.4 Displays of Treatment-Emergent Adverse Events (Japanese)

Analysis Set:	Safety Analysis Set
Analysis	
Variable(s) :	TEAE
Analytical	
Method(s) :	The following TEAEs will be summarized in the same way as in section
	6.1.2. All SOC and PT will be presented in Japanese.
	(1) Treatment-Emergent Adverse Events by Preferred Term
	(2) Drug-Related Treatment-Emergent Adverse Events by Preferred Term
	(3) Treatment-Emergent Adverse Events with Intensity of Grade 3 or
	Higher by System Organ Class and Preferred Term
	(4) Treatment-Emergent Adverse Events Leading to Study Drug
	Discontinuation by System Organ Class and Preferred Term
	(5) Serious Treatment-Emergent Adverse Events by System Organ Class

7 Significance Level and Confidence Coefficient (Part A and Part B)

and Preferred Term

• Confidence coefficient: 95% (two-sided)

Amendment History

Version	Date	Author	Detailed Description of Amendments to Text
1	April 16, 2015		Not applicable
2	July 20, 2017		Refer to Appendix 1.

Page	Existing Text	Revised Text	Rationale for Amendment
Cover			Updated in accordance with the current organization.
Cover			Updated in accordance with the current organization.
4	Glossary	Glossary	Added to clearly define the
	Descriptive statistics: number of subjects, mean,	Descriptive statistics: number of subjects, mean,	abbreviation.
	standard deviation, maximum, minimum, and quartiles	standard deviation (SD), maximum (max), minimum (min), and quartiles	
4	Glossary	Glossary	Added to clearly define the
	(New)	CV: coefficient of variation	abbreviation.
4	Glossary	Glossary	Added to clearly define the
	(New)	PK: pharmacokinetic	abbreviation.
6	Definition of Visit Window	Definition of Visit Window	Corrected to a more appropriate
	<part a=""> Pharmacokinetic Assessments</part>	<part a=""> Pharmacokinetic Assessments</part>	expression.
	Headers of the table: Visit, Scheduled Study Day	Headers of the table: Visit, Scheduled Study Time	

Appendix 1. Amendments from the Previous Version

Page	Existing Text	Revised Text	Rationale for Amendment
	(days), Scheduled Study Time (hours), and Time	(hours), and Time Interval (Study Day (days), Study	
	Interval (Study Day (days), Study Time (hours))	Time (hours))	
6	Definition of Visit Window	Definition of Visit Window	Corrected to a more appropriate
	<part a=""> Pharmacokinetic Assessments</part>	<part a=""> Pharmacokinetic Assessments</part>	expression.
		The visit windows in the whole table were revised.	
11	Definition of Visit Window	Definition of Visit Window	Corrected to a more appropriate
	<part b=""> Pharmacokinetic Assessments</part>	<part b=""> Pharmacokinetic Assessments</part>	expression.
	Headers of the table: Visit, Scheduled Study Day	Headers of the table: Visit, Scheduled Study Time	
	(days), Scheduled Study Time (hours), and Time	(hours), and Time Interval (Study Day (days), Study	
	Interval (Study Day (days), Study Time (hours))	Time (hours))	
11	Definition of Visit Window	Definition of Visit Window	Corrected to a more appropriate
	<part b=""> Pharmacokinetic Assessments</part>	<part b=""> Pharmacokinetic Assessments</part>	expression.
		The visit windows in the whole table were revised.	
20	Others	Others	Corrected according to the latest
	PK parameters	The symbols and the definitions of PK parameter were	standard PK terminology
		revised.	
20	Others	Others	Deleted unnecessary PK parameters
	AUC(0-inf) Area under the plasma/blood/serum	(deleted)	
	concentration-time curve from time 0 to infinity,		
	calculated as AUC(0-inf)=AUC(0-tlqc)+lqc/ λz , where		
	tlqc is the time of last quantifiable concentration and		
	lqc is the last quantifiable concentration.		

Page	Existing Text	Revised Text	Rationale for Amendment
	AUMC(0-inf) Area under the first moment		
	plasma/blood/serum concentration-time curve from		
	time 0 to infinity, calculated as		
	AUMC(0-inf)=AUMC(0-tlqc)+lqc×tlqc/ λ z+lqc/ λ z2,		
	where tlqc is the time of last quantifiable concentration		
	and lqc is the last quantifiable concentration.		
20	Others	Others	Corrected to a more appropriate
	Cmax/DDose-adjusted Cmax.	C _{max, ss} /DDose-normalized C _{max, ss} .	expression.
20	Others	Others	Deleted unnecessary PK parameters
	MRT Mean residence time, calculated as	(deleted)	
	MRT=AUMC(0-inf)/AUC(0-inf).		
20	Others	Others	Corrected to a more appropriate
	Vss/F Apparent volume of distribution at steady state	V_z/F_{ss} Apparent volume of distribution during the	expression.
	after extravascular administration, calculated as Vss/F=	terminal disposition phase after extravascular	
	CL/F×MRT.	administration, calculated using AUC_{τ}	
36	3.2.1 Plasma Concentrations	3.2.1 Plasma Concentrations	Corrected to clarify which descriptive
	Descriptive statistics, geometric mean, and coefficient	Number of subjects, mean, SD, min, median, max,	statistics and linear plots will be
	of variation will be used to summarize plasma	geometric mean, and CV will be used to summarize	provided.
	concentrations at each visit. Plasma concentration-time	plasma concentrations at each visit for each treatment	
	profiles will be provided for each treatment group	group.	
	using individual or mean concentrations.	Linear plots of plasma concentration-time profiles will	
		be provided for each treatment group using individual	

Page	Existing Text	Revised Text	Rationale for Amendment
		and mean (SD) concentrations in separate plots. Mean	
		(SD) plots will include the plasma concentration plot	
		for all visits, separate plots for each of Day 1, Day 14,	
		Day 28, and a plot for the plasma trough	
		concentrations.	
36	(New)	Listing	Added to separate the listing for PK
		Analysis Set: Full Analysis Set	parameters from the table of
		Analysis Variable(s) :	descriptive statistics. PK parameter
		D1: AUC _{τ} , C _{max} and t _{max}	calculation methods were also moved
		D14: AUC _{last, ss} , AUC _{τ, ss} , AUC _{τ, ss} /D, C _{max, ss} , C _{max, ss} /D,	to this new section.
		C _{min, ss} , t _{max, ss}	
		D28: AUC _{last, ss} , AUC _{τ, ss} , AUC _{τ, ss} /D, CL/F _{ss} , C _{max, ss} ,	
		$C_{max, ss}/D, t_{max, ss}, t_{1/2z}, V_z/F_{ss}, \lambda_z$, number of data points	
		with first and last data points used in the terminal	
		disposition phase regression analysis and adjusted R ²	
		(coefficient of determination) for the terminal	
		disposition phase regression analysis	
		Analytical Method(s) :	
		PK parameters will be calculated by using individual	
		plasma concentrations with actual sampling times.	
		Plasma concentrations from D1 to D2, D14 to D15 and	
		D28 to D35 will be used for the calculation of PK	

Page	Existing Text	Revised Text	Rationale for Amendment
		parameters on D1, D14 and D28 respectively. Plasma	
		concentrations deviated from the visit window will be	
		also used for the calculation. A standard	
		non-compartmental analysis will be performed using	
		the linear trapezoidal rule. If subject received	
		prohibited concomitant medications, therapies or foods,	
		then the plasma concentrations measured on and after	
		this day will be used to estimate the PK parameters for	
		the listing but the results will be treated as reference	
		values.	
		Individual PK parameters will be listed. The listings	
		will include the treatment group, subject ID and	
		evaluation day (D1, D14, and D28) in addition to the	
		PK parameters.	
37	Descriptive Statistics	Descriptive Statistics	Added the dose-normalized PK
	D1: AUC(0-24), Cmax and Tmax	D1: AUC _{τ} , C _{max} and t _{max}	parameters ($C_{max, ss}/D$ and $AUC_{\tau, ss}/D$)
	D14: AUC(0-tlqc), AUC(0-tau), AUC(0-tau)/D, Cmax,	D14: AUC _{last, ss} , AUC _{τ, ss} , AUC _{τ, ss} /D, C _{max, ss} , C _{max,}	and corrected PK parameter symbols
	Cmax/D, Cmin, Tmax	ss/D, C _{min, ss} , t _{max, ss}	according to the latest standard PK
	D28: AUC(0-tlqc), AUC(0-tau), CL/F, Cmax, Tmax,	D28: AUC _{last, ss} , AUC _{τ, ss} , AUC _{τ, ss} /D, CL/F _{ss} , C _{max, ss} ,	terminology.
	T1/2, Vss/F	$C_{max, ss}/D, t_{max, ss}, t_{1/2z}, V_z/F_{ss}, \lambda_z$	
37	Descriptive Statistics	Descriptive Statistics	Corrected to specify which
	Pharmacokinetic (PK) parameters will be calculated by	For the pharmacokinetic parameters, the number of	descriptive statistics will be provided.

Page	Existing Text	Revised Text	Rationale for Amendment
	using individual plasma concentrations with actual	subjects, mean, SD, min, median, max, geometric	The rules for data handling and the
	sampling times. Plasma concentrations from D1 to D2,	mean, and CV will be provided for each treatment	method for dose-proportionality
	D14 to D15 and D28 to D35 will be used for the	group. PK parameters which are treated as reference	assessment were changed to what
	calculation of PK parameters on D1, D14 and D28	values will be excluded from the summary statistics.	was considered more appropriate.
	respectively. Plasma concentrations deviated from the	Graphical assessment of dose-proportionality on C_{max} ,	
	visit window will be also used for the calculation. A	$_{ss}$ and $AUC_{\tau,ss}$ will be conducted on D14 and D28 by	
	standard non-compartmental analysis will be	plotting individual dose-normalized exposure	
	performed. The listing of calculated PK parameters	parameters, i.e., $C_{max, ss}/D$ or AUC _{r, ss} /D versus dose.	
	will be prepared for each subject. Descriptive statistics,		
	geometric mean, and coefficient of variation will be		
	used to summarize each pharmacokinetic parameter for		
	each treatment group. Graphical assessment of		
	dose-linearity on Cmax or AUC(0-tau) will be		
	conducted on D14 and D28.		
39	3.4.2 Handling of Dropouts or Missing Data	3.4.2 Handling of Dropouts or Missing Data	Added to define the rules for
	(New)	Values less than the lower limit of quantification will	handling values less than the lower
		be treated as zero except for the calculation of	limit of quantification.
		geometric mean for plasma concentration of TAK-385.	
		For the geometric mean, values less than the lower	
		limit of quantification will be treated as missing.	
41	4.1.2 QOL Assessment	4.1.2 QOL Assessment	Appendix containing details on the
	The following analysis will be performed using the full	The following analysis will be performed using the full	scoring procedures was added.

Page	Existing Text	Revised Text	Rationale for Amendment
	analysis set.	analysis set. The scoring procedures are described in	
		detail in the Appendix.	
41	4.2.1 Plasma Concentrations	4.2.1 Plasma Concentrations	Corrected to a more appropriate
	Descriptive statistics, geometric mean, and coefficient	Descriptive statistics, geometric mean, and CV will be	expression.
	of variation will be used to summarize plasma	used to summarize plasma concentrations at each visit	
	concentrations at each visit. Plots of plasma	for each treatment group. Case plots as well as the	
	concentrations at each visit will be provided for each	mean and standard deviation plots of changes over time	
	treatment group using individual or mean	will be provided for plasma concentrations for each	
	concentrations.	treatment group.	
42	4.3.1 Serum Testosterone Concentrations	4.3.1 Serum Testosterone Concentrations	Added to align with other similar
	(2) High-sensitivity Serum Testosterone (ng/dL)	(2) High-sensitivity Serum Testosterone	expressions.
		Concentrations (ng/dL)	
42	4.3.1 Serum Testosterone Concentrations	4.3.1 Serum Testosterone Concentrations	Added to clarify which analysis will
	Case plots as well as the mean and standard deviation	Case plots as well as the mean and standard deviation	include the reference line.
	plots of changes over time will be provided for	plots of changes over time will be provided for	
	observed values for each treatment group. A reference	observed values for each treatment group. For (1), a	
	line will be drawn where the serum testosterone	reference line will be drawn where the serum	
	concentration is 0.5 ng/mL.	testosterone concentration is 0.5 ng/mL.	
44	4.4.2 Handling of Dropouts or Missing Data	4.4.2 Handling of Dropouts or Missing Data	Added to define the rules for
	(New)	Values less than the lower limit of quantification will	handling values less than the lower
		be treated as zero for the calculation of descriptive	limit of quantification.
		statistics except for geometric mean for plasma	

Page	Existing Text	Revised Text	Rationale for Amendment
		concentration of TAK-385. For the geometric mean,	
		values less than the lower limit of quantification will be	
		treated as missing.	
65	Appendix. Criteria for Markedly Abnormal Values and	Appendix 2. Criteria for Markedly Abnormal Values	Appendix number was updated since
	Elevated Liver Enzyme	and Elevated Liver Enzyme	Appendix 1 and 3 were added to the
			SAP.
70	(New)	Appendix 3. QOL Scoring Procedures	Added Appendix 3 to make clear of
			each of the QOL scoring procedures.

Appendix 2. Criteria for Markedly Abnormal Values and Elevated Liver Enzyme

(1) Criteria for Markedly Abnormal Values

1) Vital Signs, and 12-lead ECG (except Upper MAV Criteria of QTcF Interval)

For each parameter, all evaluable data (i.e., non-missing and acceptable according to the Handling Rules for Analysis Data) obtained after baseline will be classified as a MAV or not. The criteria in the table below will be used. The lower limit of the normal range and the upper limit of the normal range are abbreviated as LLN and ULN.

Vital Signs

			MAV Criteria	
Parameter	Gender	ender Age	Lower Criteria	Upper Criteria
Systolic Blood Pressure (mmHg)	-	-	<85	>180
Diastolic Blood Pressure (mmHg)	-	-	<50	>110
Pulse (bpm)	-	-	<50	>120
Body Temperature (°C)	-	-	<35.6	>37.7

12-lead ECG

D			MAV Criteria	
Parameter	Gender Age	Lower Criteria	Upper Criteria	
Heart Rate (bpm)	-	-	<50	>120
QT Interval (msec)	-	-	<=50	>=460
QTcF Interval (msec)	-	-	<=50	_

Classifying Subjects for the Overall Treatment Period

For each parameter and subject, classifications will be made according to the conditions i) to iii) provided below. The lower and the upper criteria will be considered separately.

- i) A subject with at least one evaluable data after baseline that meets the MAV criteria will be classified as a subject with MAV.
- ii) A subject who does not meet condition i) and has at least one evaluable data after baseline that doesn't meet the MAV criteria will be considered as a subject without MAV.
- iii) A subject who does not meet conditions i) or ii) will be excluded from the analysis of MAV for that parameter.

2) 12-lead ECG (Upper MAV Criteria of QTcF Interval)

All evaluable data (i.e., non-missing and acceptable according to the Handling Rules for Analysis Data) obtained after baseline will be classified as a MAV or not. The criteria in the table below will be used. Note that the observed value and the change from baseline used for classification should be measurements taken on the same day.

		ender Age	MAV Criteria		
Parameter	Gender		Lower Criteria	Upper Criteria	
QTcF Interval (msec)	-	-	-	If either of the following conditions is met: - observed value >=500 - change from baseline >= 30 and observed value >=450	

Classifying Subjects for the Overall Treatment Period

For each subject, classifications will be made according to the conditions i) to iii) provided below.

- i) A subject with at least one evaluable data after baseline that meets the MAV criteria will be classified as a subject with MAV.
- ii) A subject who does not meet condition i) and has at least one evaluable data after baseline that meets any of the following will be considered as a subject without MAV.
 - Observed value is less than 450 msec and not missing.
 - Change from baseline is less than 30 msec and not missing, and observed value is less than 500 msec and not missing.
- iii) A subject who does not meet conditions i) or ii) will be excluded from the analysis of MAV.

(2) Criteria for Elevated Liver Enzyme

All evaluable data (i.e., non-missing and acceptable according to the Handling Rules for Analysis Data) obtained after baseline will be used to determine whether each criteria for elevated liver enzyme in the table below is met or not. If there is more than one parameter that need to be considered for a criteria, parameter measurements taken on the same day will be used. The following abbreviations are used: LLN for lower limit of the normal range, ULN for upper limit of the normal range, ALT for alanine aminotransferase, AST for aspartate aminotransferase, Tbili for total bilirubin, and ALP for alkaline phosphatase.

	Criteria for Elevated Liver Enzyme			
Label	(a) Elevated	(b) Not Elevated		
ALT > 3xULN	ALT is greater than 3 times the ULN	ALT is non-missing and less than or equal to 3 times the ULN		
ALT > 5xULN	ALT is greater than 5 times the ULN	ALT is non-missing and less than or equal to 5 times the ULN		
ALT > 8xULN	ALT is greater than 8 times the ULN	ALT is non-missing and less than or equal to 8 times the ULN		
ALT > 3xULN with Tbili > 2xULN	ALT is greater than 3 times the ULN and the total bilirubin is greater than twice the ULN	Either ALT is non-missing and less than or equal to 3 times the ULN, or the total bilirubin is non-missing and less than or equal to twice the ULN		
AST > 3xULN	AST is greater than 3 times the ULN	AST is non-missing and less than or equal to 3 times the ULN		
AST > 5xULN	AST is greater than 5 times the ULN	AST is non-missing and less than or equal to 5 times the ULN		
AST > 8xULN	AST is greater than 8 times the ULN	AST is non-missing and less than or equal to 8 times the ULN		
AST > 3xULN with Tbili > 2xULN	AST is greater than 3 times the ULN and the total bilirubin is greater than twice the ULN	Either AST is non-missing and less than or equal to 3 times the ULN, or the total bilirubin is non-missing and less than or equal to twice the ULN		
ALT or AST > 3xULN	Either ALT or AST is greater than 3 times the ULN	Both ALT and AST are non-missing and less than or equal to 3 times the ULN		
ALT or AST > 5xULN	Either ALT or AST is greater than 5 times the ULN	Both ALT and AST are non-missing and less than or equal to 5 times the ULN		
ALT or AST > 8xULN	Either ALT or AST is greater than 8 times	Both ALT and AST are non-missing and		

	Criteria for Elevated Liver Enzyme		
Label	(a) Elevated	(b) Not Elevated	
	the ULN	less than or equal to 8 times the ULN	
ALT or AST > 3xULN with Tbili > 2xULN	Either ALT or AST is greater than 3 times the ULN and the total bilirubin is greater than twice the ULN	 If any of the following conditions is met: Both ALT and AST are non-missing and less than or equal to 3 times the ULN. Total bilirubin is non-missing and less than or equal to twice the ULN. 	
ALT and AST > 3xULN	Both ALT and AST are greater than 3 times the ULN	Either ALT is non-missing and less than or equal to 3 times the ULN, or AST is non-missing and less than or equal to 3 times the ULN	
ALT and AST > 5xULN	Both ALT and AST are greater than 5 times the ULN	Either ALT is non-missing and less than or equal to 5 times the ULN, or AST is non-missing and less than or equal to 5 times the ULN	
ALT and AST > 8xULN	Both ALT and AST are greater than 8 times the ULN	Either ALT is non-missing and less than or equal to 8 times the ULN, or AST is non-missing and less than or equal to 8 times the ULN	
ALT and AST > 3xULN with Tbili > 2xULN	Both ALT and AST are greater than 3 times the ULN and the total bilirubin is greater than twice the ULN	 If any of the following conditions is met: ALT is non-missing and less than or equal to 3 times the ULN AST is non-missing and less than or equal to 3 times the ULN Total bilirubin is non-missing and less than or equal to twice the ULN 	
ALP > 3xULN	ALP is greater than 3 times the ULN	ALP is non-missing and less than or equal to 3 times the ULN	
ALP > 3xULN with ALT > 3xULN	Both ALP and ALT are greater than 3 time the ULN	Either ALP is non-missing and less than or equal to 3 times the ULN, or ALT is non-missing and less than or equal to 3 times the ULN	
ALP > 3xULN	Both ALP and AST are greater than 3	Either ALP is non-missing and less than or	

	Criteria for Elevated Liver Enzyme		
Label	(a) Elevated	(b) Not Elevated	
with AST > 3xULN	times the ULN	equal to 3 times the ULN, or AST is	
		non-missing and less than or equal to 3	
		times the ULN	

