#### 4.1.2.5 Overseas Phase 1 Single- and Multiple-dose Study (TAK-385\_C27001)

Study C27001 was a phase 1 study that evaluated the safety, tolerability, PK, and PD of TAK-385 in 176 healthy English adult male subjects (128 subjects received TAK-385) receiving single doses of TAK-385 up to 360 mg QD and multiple doses of TAK-385 up to 180 mg QD for up to 28 days. The study had 4 parts: Part 1 included single-dose administration of TAK-385 to 32 subjects across 4 dose cohorts plus placebo and had a fed/fasted arm; Part 2 included multiple dose administration of TAK-385 for 14 days to 40 subjects across 5 dose cohorts plus placebo; and Parts 3 and 4 included multiple dose administration of TAK-385 for 28 days to 66 and 38 subjects, respectively, across 2 dose cohorts (a total of 4 dose levels), plus placebo.

There were no deaths or SAEs following single-dose or multiple-dose treatment with TAK-385 for 14 or 28 days.

Following 28 days of QD dosing, there were 3 discontinuations due to drug-related, hepatic AEs: 2 subjects in the 160 mg dose cohort in Part 3 of the study discontinued treatment due to Grade 1 AEs of hepatic enzyme increased (ALT and AST); and 1 subject in the 60 mg dose cohort in Part 4 of the study discontinued treatment due to a Grade 2 AE of liver function test (LFT) abnormal (ALT and AST). There was no clear trend between dose level and toxicity, although abnormal liver transaminase levels appeared more likely to occur within 2 weeks at higher dose levels. All AEs resolved by the end of the study.

The majority of subjects had at least 1 AE, but no increase in the incidence of AEs with increasing dose of TAK-385 was observed. The most common AEs observed across all dose cohorts were bradycardia, hot flush, and headache, and the most common, drug-related AE was hot flush.

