  - b. Patients with uncontrolled hypertension (systolic blood pressure > 150 mmHg and diastolic blood pressure > 90 mmHg at 2 separate measurements taken no more than 60 minutes apart at screening). Patients whose blood pressure is brought under control by antihypertensive medication may be rescreened.
  - c. Patients with myocardial infarction, unstable symptomatic ischemic heart disease, arrhythmias of CTCAE Grade > 2, thromboembolism (deep vein thrombosis, pulmonary embolism, or symptomatic cerebrovascular events), or other heart diseases (eg, pericardial effusion, restrictive cardiomyopathy). However, chronic stable atrial fibrillation controlled by stable anticoagulant therapy will be allowed.
13. Patients with bilateral hydronephrosis or bladder neck outlet obstruction.
  14. Known hypersensitivity to TAK-385, TAK-385 excipients, or GnRH antagonists.
  15. Patients with a past history of gastrointestinal tract treatments (including gastrectomy) or gastrointestinal disease that could affect the drug absorption or tolerability (malabsorption, esophageal reflux, peptic ulcer, erosive esophagitis).
  16. Patients positive for hepatitis B surface antigens (HBsAg), hepatitis C virus (HCV) antibodies, human immunodeficiency virus (HIV) antibodies, or serologic test for syphilis, or with life-threatening disease other than cancer, at screening.
  17. Clinically relevant ECG abnormalities, or the following ECG abnormalities, at screening.
    - a. Q-wave infarction, unless identified 6 or more months prior to TAK-385 treatment initiation
    - b. QTcF interval > 450 msec (when calculating the QTc interval, Fridericia's equation  $[QT/RR^{0.33}]$  will be used)
  18. Patients with congenital QT prolongation.
  19. Current use of Class 1A or Class 3 antiarrhythmic medications.
  20. New York Heart Association [18] Class III or IV heart failure ([Appendix H](#)).
  21. Patients with clinical laboratory abnormalities suggesting clinically relevant underlying disease, or with any of the following abnormal results, at screening.
    - Serum creatinine  $\geq 2.0$  mg/dL
    - ALT or AST  $\geq 1.5 \times$  ULN for the investigational site
    - Total bilirubin  $\geq 2 \times$  ULN for the investigational site
    - Neutrophil count < 1,500/mm^3, platelet count < 100,000/ $\mu$ L, hemoglobin < 10.0 g/dL

- Results of heart-related tests (creatine kinase MB [CK-MB] and cardiac troponin T) exceeding the investigational sites reference value.

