#### 3) Clinical laboratory tests, vital signs, and 12-lead ECG

The following analysis will be performed for the safety analysis set.

For continuous data, descriptive statistics for observed values at baseline and at each assessment time point as well as for the change from baseline will be calculated by part and by dose.

Cross tables for the results of the assessment of each test parameter based on discrete data and reference values before and after study drug treatment (such as the determination of

whether results are normal or abnormal, or qualitative laboratory values) will be prepared by part and by dose.

[Other endpoints]

- Bone mineral density

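### Apart from upper QTcF, the markedly-abnormal-value tables for vital signs and ECG take no account of baseline, so abnormalities present before dosing and new ones are counted together

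*SAP*

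**What the plan says.** SAP Appendix 2 (1) 1) sets fixed limits for markedly abnormal values (MAVs):

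- systolic pressure below 85 or above 180 mmHg
- diastolic pressure below 50 or above 110 mmHg
- pulse and ECG heart rate below 50 or above 120 bpm
- temperature below 35.6 or above 37.7 °C
- uncorrected QT at or below 50 or at or above 460 msec
- QTcF at or below 50 msec

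The rule for a subject is "A subject with at least one evaluable data after baseline that meets the MAV criteria will be classified as a subject with MAV". A man who does not meet that condition but "has at least one evaluable data after baseline that doesn't meet the MAV criteria will be considered as a subject without MAV". Neither rule refers to the baseline value.

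Upper QTcF is handled separately in Appendix 2 (1) 2). A value is an MAV if it is at least 500 msec, or if "change from baseline >= 30 and observed value >=450". The rule for a man without an MAV also uses baseline: "Change from baseline is less than 30 msec and not missing, and observed value is less than 500 msec and not missing" is one of its two alternatives.

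SAP Sections 5.3.2.1, 5.3.2.2, 6.3.2.1 and 6.3.2.2 report MAVs as overall frequencies by treatment group. No baseline MAV count or shift is specified. The same sections also plan change from baseline by visit, individual plots over time, QTcF and QTcB change categories, and a shift table for the ECG interpretation.

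Protocol Section 13.1.7 3) covers laboratory tests, vital signs and ECG together, and plans "Cross tables for the results of the assessment of each test parameter based on discrete data and reference values before and after study drug treatment".

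**The concern.** Vital signs and 12-lead ECGs are primary endpoints in both parts (Protocol Section 5.2.1). Every subject is to receive TAK-385, so there is no untreated group, and a man's own baseline is the natural reference for judging whether an abnormality is new. A count that mixes new abnormalities with those already present answers a less useful question than the one a reader will bring to it.

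Pulse and heart rate show this best. In the earlier study in healthy men (Protocol Section 4.1.2.5), "The most common AEs observed across all dose cohorts were bradycardia, hot flush, and headache". A table of men with a rate below 50 bpm will therefore be read closely, and it should show how many were below 50 bpm before the first dose.

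The special rule for upper QTcF shows that the authors did consider baseline for one parameter. The SAP gives no reason for leaving it out of the others.

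**Working it through.** **The plan's own figure.** The plan gives no figure for MAVs. Its one design figure (Protocol Section 13.3) is an approximately 80% chance of detecting an adverse event with 10% true incidence in 15 subjects. It reproduces as 1 − 0.9^15 = 0.794. The present point does not depend on it.

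**Can an eligible man already meet an MAV limit?** Protocol Section 7.2 excludes "QTcF interval > 450 msec" but sets no limit on uncorrected QT. The protocol's Fridericia form is QTcF = QT / RR^0.33, so QT = QTcF × (60/HR)^0.33.

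| QTcF (msec) | Heart rate (bpm) | QT (msec) | At or above 460? |
|---|---|---|---|
| 450 | 57 | 457.7 | no |
| 450 | 56 | 450 × (60/56)^0.33 = 460.4 | yes |
| 450 | 55 | 463.1 | yes |
| 450 | 50 | 477.9 | yes |
| 440 | 50 | 440 × (60/50)^0.33 = 467.3 | yes |

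At QTcF 450 the limit is reached once RR is at least (460/450)^(1/0.33) = 1.069 s, a heart rate of about 56 bpm or lower.

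- Blood pressure: the numeric part of exclusion 12b requires "systolic blood pressure > 150 mmHg and diastolic blood pressure > 90 mmHg" at two measurements. A man at 185/85 exceeds the first limit but not the second, so 12b is not triggered, yet he is past the systolic MAV limit of 180.
- Pulse, temperature and low blood pressure: no numeric entry limit.

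**Upper QTcF, for contrast.** A man with a baseline of 450 msec must reach 480 to satisfy the change-based condition. The 500 msec condition has no baseline term, but a man screened at 450 or below must rise by at least 50 msec to meet it. Carry-over from the screening value is effectively excluded.

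**Must he meet the limit again?** Yes. Baseline status alone counts no one. A single later value is enough, however, and Section 6.3.2.1 lists 12 post-baseline vital-sign visits for a man who stays to Week 97 and attends safety follow-up. If his chance of crossing the limit were 10% or 30% per visit (assumed, visits independent), the chance of at least one crossing is 1 − 0.9^12 = 72% or 1 − 0.7^12 = 99%.

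**Size.** One such man adds 1/15 = 6.7 points in a Part B group, 1/6 = 16.7 points in a cohort of 6, and 1/3 = 33.3 points in a cohort of 3.

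The documents give no baseline frequency. Let b be the assumed share of men who meet a limit at baseline and again afterwards:

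| b | Expected such men per 15 (15b) | Chance of at least one in 15 | Chance of at least one in 3 | Reported rate, no new MAVs | Reported rate, 10% new MAVs in the rest: b + 0.1(1 − b) |
|---|---|---|---|---|---|
| 5% | 0.75 | 53.7% | 14.3% | 5% | 14.5% |
| 10% | 1.5 | 79.4% | 27.1% | 10% | 19% |
| 20% | 3.0 | 96.5% | 48.8% | 20% | 28% |

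The chances are 1 − (1 − b)^15 and 1 − (1 − b)^3. With no new MAVs, a count of new MAVs would be 0% in every row.

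**The case against.** The strongest reply is that the SAP already uses baseline in several places. Change from baseline is summarised at each visit, QTcF and QTcB changes are categorised, ECG interpretation has a shift table, and each man's values are plotted over time. With 3 to 6 men per cohort and 15 per group, a reader could trace every man with an MAV. The tables are descriptive, and no test or decision rule depends on them. This stands, and it limits the weight of the point. It does not remove it: visit means do not identify individuals, and a reader should not have to rebuild a primary-endpoint count from plots.

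A second reply is that investigator judgement may keep some of these men out. Exclusion 12 covers uncontrolled, clinically significant circulatory disorders, 17 covers clinically relevant ECG abnormalities, and 22 covers clinical problems found at examination or on ECG. This also stands. A man at 185/85 might be excluded that way; an asymptomatic pulse of 48 need not be.

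A reader might also infer that the SAP breaches Protocol Section 13.1.7 3), since vital signs get no before-and-after table. That is arguable only. The protocol's examples are normal/abnormal determinations and qualitative laboratory values, vital signs are collected as plain numbers, and the MAV limits first appear in the SAP. The ECG interpretation, which is a normal/abnormal assessment, does get its table.

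**Conclusion.** The point holds for systolic and diastolic pressure, pulse, temperature, ECG heart rate, uncorrected QT and lower QTcF. For these, a man who met a limit before dosing and meets it again is counted as if the abnormality were new, and the numeric entry criteria do not prevent it. The size per man is certain: about 7 points in a group of 15 and 33 in a cohort of 3. The number of such men is unknown, so the 5% to 20% range above is illustrative.

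Three stronger readings are not supported:

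- That ECG MAVs as a whole ignore baseline. Upper QTcF uses change from baseline, and the entry limit protects its 500 msec condition.
- That the SAP cannot separate new from pre-existing findings. The other outputs do so in part.
- That the tables overstate drug-related findings. They are not labelled drug-related or treatment-emergent; related events have their own tables.

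The conclusion assumes that the separate Handling Rules for Analysis Data add no baseline condition. The SAP cites them for whether a value is evaluable and does not say that they contain one. This is an improvement to descriptive tables at almost no cost, not a flaw in the trial's conclusions.

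**What to change.** In SAP Sections 5.3.2.1, 5.3.2.2, 6.3.2.1 and 6.3.2.2, for every MAV criterion except upper QTcF:

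1. Keep the overall count as planned.
2. Add a cross-tabulation, by treatment group, of baseline status (criterion met, not met, or baseline missing) against post-baseline status (met at least once, or never met).
3. Report new MAVs as the men who meet the criterion after baseline among those who did not meet it at baseline and have at least one evaluable later value, with that group as the denominator. Treat lower and upper limits separately, as Appendix 2 already does.

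Baseline can follow the existing windows for vital signs and ECG (Study Day −28 to 1). Upper QTcF can stay as written. The cost is a few lines in Appendix 2 and the four sections, and a small addition to each table. No extra data or visits are needed.
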